This is the first study that we are aware of that will look at the use of Aeroneb system to deliver bronchodilator therapy in asthma exacerbations.

The study will provide novel data to demonstrate whether the use of Aeroneb system to deliver bronchodilator therapy is advantageous to patients with severe asthma exacerbations.

If the hypothesis is proven to be correct this will mean improved patient's outcomes in severe asthma exacerbations and potentially shorter ER stay, reduction in the hospitalization rate and cost of care.

III. Research Plan

A. Experimental design:

This is a prospective, single blinded, parallel, single center, randomized controlled clinical trial (n=68). Upon entry into the study, patients will be randomized to two groups:

Treatment group: All the bronchodilator therapies during the ER visit (albuterol and ipratropium) will be delivered via Aeroneb nebulizer system. The asthma management will be as per the adult asthma protocol in the ER.

Control group: All the bronchodilator therapies (Albuterol and ipratropium) will be delivered via small volume jet nebulizer system, which is currently the standard nebulizer device used in the emergency department at Tufts Medical Center. The asthma management will be as per the adult asthma protocol in the ER.

B. Sample size and statistical analysis(es):

Upon entry into the study patients will be randomized at a 1:1 ratio with permuted block design of 6 to one of the 2 groups. Randomization will be conducted using a computerized randomization scheme and secured in a sealed envelope for allocation.

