For a power calculation to determine the sample size, historical data was utilized from prior clinical study that examined the effect of bronchodilator (B2-agonist) treatment on the improvement of the peak flow measurement after 30 minutes of the initial bronchodilator treatment⁴. In this study, the mean PEFR improved from 27% to 39% at 30 minutes after the initial bronchodilator treatment. We hypothesize that mean PEFR of the intervention group at 30 minutes of the bronchodilator therapy will be at least 10 points higher than the control group (i.e. mean PEFR \geq 49% at 30 minutes of the initial bronchodilator therapy). Group sample sizes of 34 and 34 is required to achieve a power $> 80\%$ to reject the null hypothesis of equal means when the groups mean difference is 10.0 with a standard deviation for both groups of 14.4 and with a significance level (alpha) of 0.050 using a two-sided two-sample equal-variance t-test.

Taking into consideration the screen failures the disqualification and drop-outs, we are anticipating enrolling around 110 patients in order to have 68 patients who will complete the study objectives.

For the statistical analysis treatment evaluations will be performed on the principle of intention to treat (ITT) using the data collected from all randomized participants who completed the study procedures including the two parts of the informed consent form (ICF). Demographics and baseline characteristics of patients will be summarized for each group. Continuous variables will be reported as mean \pm standard deviation, with minimum, median, and maximum values.

Categorical variables will be reported as n and %. All statistical testing will be two-sided with alpha=0.05.

For the primary outcome, mean PEFR at 30 minutes post-bronchodilator treatment, analysis of covariance (ANCOVA) with adjustment for baseline PEFR will be utilized.

ANCOVAs with adjustment for baseline values, and incorporating repeated measures where appropriate, will be utilized for the following secondary outcomes: absolute value of PEFR (L/Min) at 30 minutes, PEFR percentage of predicted at 60 minutes and 180 minutes, FEV1 percentage of predicted as well as absolute FEV1 (L/Sec) at 30 minutes, 60 minutes and 180 minutes, Borg dyspnea score at 30 minutes, 60 minutes and 180 minutes, accessory muscle use score at 30 minutes, 60 minutes and 180 minutes, and heart rate at 30 minutes, 60 minutes and 180 minutes.

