3.3 Upon disposition from the ER
The following data will be collected: the disposition location (home, floor or ICU), length of stay in the ER (from ER arrival time to the disposition order placement time), intubation in the ER, need for NIV ventilation, number and total doses of albuterol treatments in the ER and number and total doses of ipratropium in the ER.

F. Assessment of Subject Safety and Development of a Data and Safety Monitoring Plan

1. Definition of Serious Adverse Event (SAE) and Adverse Event (AE) for this study:
For the purposes of this study a SAE is a serious adverse event that is life-threatening or results in death, hospitalization or prolonged hospitalization, significant disability/incapacitation, congenital anomaly or birth defects, or may jeopardize the subject's health and may require medical or surgical intervention to prevent one of the other listed outcomes. A SAE does not necessarily have to have a causal relationship with the study treatment. SAE may not be uncommon in the study due to the acute nature of patients presenting with severe asthma exacerbations that may be enrolled into the study. The study will be conducted in the emergency room, which provides a high level of monitoring and is capable of managing SAE in this acute patient group. It is possible that the Aeroneb group patients may experience more frequent side effects related to potentially more albuterol and ipratropium delivery and those side effects may include arrhythmia and tremor. Those side effects will be monitored closely and patients will be placed on continuous cardiac monitoring during the ER visit to capture any arrhythmia.
2. Reporting timeframe for SAEs and AEs:
SAEs will be reported to the IRB within five business days of the event occurring. The investigators will record and track any SAE or AE that might occur during the study. If a disproportionate number of events occur in either of the groups, then the study will be stopped. A "disproportionate number" is defined as one showing a statistically significant difference in SAEs and AEs occurrence after the recruitment of half the sample size (34 patients).
3. Accountability procedures as they relate to drugs, devices, and data:
The Principal Investigator [name] and the research team member [name] will be accountable for the study and interface with Aerogen, the study sponsor.
4. Data and Safety Monitoring Plan:

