We do not anticipate serious complications attributable to the device, but will monitor patients for potential adverse effects such as discomfort or cough. Any serious adverse events that occur during use are more likely due to the underlying disease than the device itself, but will be reported promptly to the IRB by the investigators per the reporting timeframes described above.

The Research team will report to the IRB the process of the informed consent after enrolling 10 patients (if this occurs before the study continuing review).

G. Subject Participation

1. Recruitment:

Patients presenting with severe asthma exacerbation to Tufts Emergency Room will be recruited on to the study. Patients who meet any exclusion criteria will not be screened for possible enrollment. Patients will be approached at their bedside by the PI, co-investigator or research coordinator. No advertisements will be used.

2. Registration:

Patients, that can potentially take part in the study, will be assessed by the PI or the co-investigator for their ability to fulfill the eligibility criteria and meet the exclusion criteria, as listed above.

3. Screening Interview/questionnaire: Not applicable

4. Transportation: Not applicable

5. Informed consent process and timing of obtaining of consent:

The participant must have the full mental capacity to provide the consent. The consenting process will be two steps process, each step will involve face-to-face meeting with one of the study investigators at bedside in the ER room

1-The first part of the consent will cover all the essential elements of the informed consent. Given the acuity of the medical condition, it is anticipated that the total amount of time given to this step of the informed consent will be no longer than 10 minutes. No study related procedures will be conducted until this step of the informed consent is signed off by the subject. Permission will also be obtained from the primary provider for the participation of the patient in the study before a discussion with the patient regarding consent occurs.

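### The only trial-level stopping rule joins serious and non-serious events in one undefined significance criterion at 34 patients, so expected side effects can force a stop while sensitivity to serious harm is low

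*Combined protocol and SAP*

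**What the plan says.** Section III.F.2 (Reporting timeframe for SAEs and AEs) contains the rule: "If a disproportionate number of events occur in either of the groups, then the study will be stopped". The stop is mandatory and applies to an excess in either arm. An excess of this kind "is defined as one showing a statistically significant difference in SAEs and AEs occurrence after the recruitment of half the sample size (34 patients").

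No test is named for this comparison. The only available alpha is the general statement in III.B: "All statistical testing will be two-sided with alpha=0.05". The text does not say whether patients or events are counted, whether SAEs and AEs are pooled, tested separately or must both differ, or whether testing is repeated after 34 patients.

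III.F.1 says Aeroneb patients may have more side effects, and "those side effects may include arrhythmia and tremor". III.F.4 adds that the team "will monitor patients for potential adverse effects such as discomfort or cough". III.F.1 counts hospitalization as an SAE whether or not the study treatment caused it, and accepts that SAEs may be fairly frequent. Section I puts admission at 20% to 33% of ED patients, and hospitalization is also a secondary outcome.

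No other trial-level stopping rule and no independent monitoring body is described. III.C.1(c) covers withdrawal of individual subjects only.

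**The concern.** The rule has three plausible readings, and each behaves badly.

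- **Pooled.** Common mild events enter the same count as serious ones and mask a serious excess.
- **Either class can trigger.** A side effect that the protocol already expects on Aeroneb, tremor for example, can end the trial before the primary question is answered.
- **Both classes must differ.** A serious excess alone never stops the trial.

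Two further problems follow. The unnamed test can decide the outcome by itself. And because admission is an SAE and the rule works in both directions, fewer admissions on Aeroneb, which the Outcomes section hopes for, meets the definition of disproportionate if it reaches significance.

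**Working it through.** **Plan's own figure.** III.B states "Group sample sizes of 34 and 34 is required to achieve a power" above 80%, "when the groups mean difference is 10.0 with a standard deviation for both groups of 14.4". The noncentrality is 10 / (14.4 × √(2/34)) = 2.86. The noncentral t gives power 0.805 at 34 per arm and 0.793 at 33, so 34 per arm reproduces. The safety look is at 68 / 2 = 34 patients. The plan states no error rate or power for the stopping rule.

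**Arm sizes at the look.** Patients are "randomized at a 1:1 ratio with permuted block design of 6". Thirty-four patients are five full blocks plus four, so the split is 17:17 with probability C(4,2) × C(2,1) / C(6,3) = 12/20 = 0.6, and otherwise 18:16. I use 17:17.

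**The test matters.** For 4 v 0 patients with an event:
- Fisher, two-sided: 2 × C(17,4) / C(34,4) = 2 × 2380 / 46376 = 0.103. No stop.
- Uncorrected chi-square: 34 × (4×17 − 13×0)² / (17×17×4×30) = 4.53, p = 0.033. Stop.

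The smallest differences that trigger are 5 v 0, 7 v 1, 9 v 2 and 10 v 3 by Fisher, and 4 v 0, 6 v 1, 8 v 2 and 9 v 3 by chi-square.

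**Chance of a stop.** Sum Bin(a; 17, p1) × Bin(b; 17, p0) over all (a, b) with two-sided p < 0.05. The 20% and 33% bases use the protocol's admission figure as a proxy for the SAE rate. All other rates are assumptions.

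| Serious events, tested alone | Fisher | Chi-square |
|---|---|---|
| 5% v 15% | 4.4% | 11.5% |
| 5% v 20% | 11.6% | 23.0% |
| 20% v 40% | 14% | 23% |
| 33% v 66% | 38% | 52% |

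By the normal approximation, 80% power needs 141 per arm for 5% v 15% and 82 per arm for 20% v 40%. An 18:16 split does not change the picture: 5% v 20% gives 14-19% by Fisher.

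**Pooled reading.** With independent classes, the proportion with any event is 1 − (1 − s)(1 − m), where s is the serious rate and m the mild rate.

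| s | m | Pooled | Fisher |
|---|---|---|---|
| 5% both | 20% v 30% | 24% v 33.5% | 4% |
| 5% both | 20% v 40% | 24% v 43% | 12% |
| 5% both | 20% v 60% | 24% v 62% | 51% |
| 5% v 20% | 30% both | 33.5% v 44% | 5% |

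In the last row a serious excess that would trigger 12% of the time alone triggers only 5% once pooled. The same dilution occurs within SAEs: with admission at 26% in both arms, an independent 5% v 20% excess of other serious events (29.7% v 40.8%) triggers about 5%.

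**Fewer admissions on Aeroneb.** A fall from 20% to 10% triggers a stop 5% (Fisher) or 11% (chi-square) of the time.

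**Number of looks.** With no true difference and base rates of 20-50%, one look triggers about 2% (Fisher) or 4-6% (chi-square). Testing after every pair of patients from 34 to 68 raises this to about 6-8% or 13-15% (simulation).

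**The case against.** The strongest reply is that the rule is one safeguard among several and that its weakness is easily exaggerated. SAEs go to the IRB within five business days, the treating physician can end a subject's participation, and cardiac monitoring is continuous. A sponsor may reasonably want a broad trigger, the more so because the expected effects include arrhythmia as well as tremor. These points stand, and it would be wrong to say that patients are unprotected. They do not tell anyone how to apply the rule.

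A reader might infer that the rule would almost never fire for serious harm. The documents do not support that. Admission counts as an SAE and is put at 20-33%, and a doubling from there fires the rule 14-52% of the time across the two tests. Very low power is confined to uncommon serious events, whose rates the protocol does not give.

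A reader might also infer that tremor or cough would probably stop the trial. The 51% figure needs mild events to triple from 20% to 60%; smaller imbalances give 4-12%. Cough is recorded at baseline in both arms, and nothing in the documents points to a difference between arms. If both classes must differ, a mild imbalance alone cannot stop the trial.

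Finally, a single test, a single look and a 17:17 split are readings, not text. Nor does any passage say that the blinded recording investigator is the person who compares events by arm; the protocol leaves that open.

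**Conclusion.** The point holds as a defect in the stated rule. A mandatory stop rests on a criterion that mixes serious with non-serious events, and none of its three readings gives a sound rule. Power for serious harm at this look is low, and very low for uncommon events (4% Fisher or 11.5% chi-square at 5% v 15%). Expected side effects can trigger a stop if the classes are pooled or if either suffices, with a probability that depends heavily on the size of the imbalance. A favourable difference in admissions can trigger one too.

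These sizes assume about 17 per arm, two-sided 0.05, patients as the unit and, for pooling, independence of the two classes. The uncommon-event and mild-event rates are assumptions; only the 20-33% base comes from the protocol, as a proxy. The case for redrafting does not depend on any one of these rates.

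**What to change.** Rewrite the definition of disproportionate in III.F.2:

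1. Compare serious events separately, counted as patients with at least one event, by Fisher's exact test at a stated alpha, sidedness and set of looks. Report admission for the presenting exacerbation apart from other serious events.
2. Report non-serious AEs by arm to the IRB for review, not as an automatic stop.
3. Have the by-arm table prepared by the statistician or another existing team member who does not record blinded outcomes.

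The cost is protocol wording and one short table per look. The automatic stop for non-serious events is lost, including for non-serious arrhythmia, so the IRB review must cover these.

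Alpha and sidedness are for the sponsor to choose, with the false-stop risk stated over all looks. As an illustration, one-sided Fisher at 0.10 raises detection of 5% v 20% from 12% to 28.5% at the first look, so it still misses about 71%. For equal rates of 5% to 33%, its false-stop risk is 0.4% to 5% at the first look and about 2% to 10% over three looks at 17, 22 and 28 per arm (simulation). A one-sided test also gives up the present protection against an excess in the control arm.
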